#### **4.2.4. Supplementary estimand for primary endpoint and analysis**

A supplementary estimand analysis for primary endpoint will be conducted if **cci** of participants in the ITT analysis set are unable to comply with the 2 doses of gepotidacacin before 24 hours ( $\pm$ 4 hours). Supplementary estimand analysis will be performed using ITT analysis set. Thereby including those participants who were unable to adhere to the 2 doses of treatment as prescribed before 24 hours ( $\pm$ 4 hours) and were excluded from the CE24 set. Participants who are unable to complete the CSS assessment at 24 hours ( $\pm$ 4 hours) will be considered treatment failures and included in the analysis as not improvers. Percentage of participants who achieve clinical symptom improvement along with the 95% exact Binomial CI will be produced in supplementary estimand analysis for primary efficacy endpoint.

##### **4.2.4.1. Sensitivity analysis of supplementary estimand for primary endpoint**

- A sensitivity of the supplementary estimand for primary endpoint will be performed according to the rule mentioned in Section 4.2.4. considering ITT analysis set. The multiple imputation method will be used to impute the Responders (participants who achieve clinical symptom improvement) at 24 hours ( $\pm$ 4 hours) as described in Section 4.2.3. step 1 & step 2.

Percentage of participants clinical symptom improvement at 24 hours  $\pm$  4 hours will be estimated and its corresponding 95% Exact Binomial CIs will also be presented.

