Objectives, endpoints, and estimands: The primary objective of this study is to evaluate the clinical symptom improvement with gepotidacin treatment in female participants with uUTI at (24 hours [± 4 hours]). This will be evaluated by the number of participants who achieve clinical symptom improvement (without the need for other systemic antimicrobials), defined as a decrease from Baseline in CSS total score of at least 1 point at (24 hours [± 4 hours]). For additional information on the primary, secondary, and exploratory objectives and endpoints, refer to Section 3.

[figure not shown]
Overall design: This is a Phase 3b, open-label, single-arm, multicenter study to evaluate clinical symptom improvement and the safety of gepotidacin in female participants ≥ 12 years of age with clinical symptoms and urine dipstick findings suggestive of uUTI. Participants who meet eligibility requirements will receive gepotidacin 1500 mg administered orally as 2×750 mg tablets BID for 5 days. (Note: Each dose is to be taken after food consumption and with water to assist with tolerability.) Clinical symptom and safety assessments will be conducted throughout the study. The total duration of study participation is approximately 28 days, with at least 1 planned on site study visit and 6 telephone call study contacts (see Section 1.3 and Section 8 for study visit details), with allowance for unscheduled visits. For additional information on the overall design, refer to Section 4.1.

Number of participants: Approximately 90 participants will be enrolled in the study to ensure at least 82 evaluable participants are included in the primary analysis, such that the half width of the 95% CI is approximately $\leq 10\%$, under an assumption that 74% of participants meet the primary endpoint criteria as observed in the Phase 3 studies.

Data monitoring/other committee: This will be overseen by the GSK SRT (Section 10.9.6).

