**Intercurrent Events and Strategies:**

- The ICEs and estimand strategies are as follows:
  1. Participants unable to take 2 doses as prescribed before the CSS assessment at 24 hours ( $\pm 4$  hours) (Treatment Policy Strategy). Interest lies in the treatment effect regardless of compliance with the study intervention.
  2. A participant using other systemic antimicrobials, for uUTI on or before the CSS assessment at 24 hours ( $\pm 4$  hours) and/or for other infections before the CSS assessment at 24 hours ( $\pm 4$  hours) (Composite Strategy). These ICEs are incorporated into the definition of the endpoint.

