**Intercurrent Events and Strategies:**

- The intercurrent events (ICEs) and estimand strategies are:
  1. Participants unable to take  $\geq 80\%$  doses of gepotidacin up to each time point i.e., 24 hours ( $\pm 4$  hours), 48 hours ( $\pm 4$  hours), 72 hours ( $\pm 4$  hours), and 96 hours ( $\pm 4$  hours) (Treatment Policy Strategy). Interest lies in all participants regardless of compliance with study intervention.
  2. A participant using other systemic antimicrobials (for uUTI or other infections) on or before 48 hours ( $\pm 4$  hours), 72 hours ( $\pm 4$  hours), and 96 hours ( $\pm 4$  hours) (Composite Strategy). This ICE is incorporated into the definition of the endpoint.
  3. Study intervention discontinuation (due to any reason) (Treatment Policy Strategy). Interest lies in the treatment effect regardless of study intervention discontinuation.

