#### 4.2.3. Sensitivity analyses for primary endpoint analysis

Sensitivity analysis will be conducted to examine the robustness of the primary efficacy results for the primary estimand. The sensitivity analysis will be performed using the CE24 set. A sensitivity analysis for the primary endpoint will be carried out to assess the impact for those participants who are unable to complete the CSS assessment at 24 hours ( $\pm$ 4 hours). Missing clinical improvement data (without any antibiotic use) will be imputed under the missing at random (MAR) assumption. If an antibiotic is taken for uUTI before or at the timepoint of CSS assessment and/or for other infections before the timepoint of CSS assessment, the outcome variable will be imputed as (“Participants without Clinical Improvement or Resolution”). Multiple imputation method will be implemented to impute the incomplete (missing) CSS at 24 hours ( $\pm$ 4 hours) using following steps -

Step 1: The missing clinical improvement with resolution outcome (without any antibiotics use) will be imputed using a logistic regression model. The following baseline covariates will be included in the imputation model. The number of imputations will be 1000 and SEED=219575.

- CCI
- 
- 
- 

Any participants who have a missing value for one or more model covariates listed above will be excluded from the imputation model. The participants with missing covariates will be classified as “Participants without Clinical Improvement or Resolution.”

Model for multiple imputation will be diagnosed to ensure the good fit for the data of clinical response.

Step 2: Step 1 will generate 1000 imputed datasets. From the imputed dataset, participants with clinical improvement will then be derived using the imputed and non-missing data per Section 4.2.1. and [Table 1](#)

Step 3: The estimated quantities in Step 2 will be combined across the imputed datasets using Rubin’s rules to provide pooled estimates for the clinical symptom improvement rate.

Percentage of participants with “Clinical improvement with resolution outcome” at 24 hours  $\pm$  4 hours will be estimated and its corresponding 95% (Wald) CIs will also be presented.

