#### **4.3.1.5. Sensitivity analyses of supplementary estimand for secondary endpoints**

Sensitivity of supplementary estimands analyses for secondary endpoints will be performed according to rule mentioned in Section 4.3.1.4. considering ITT analysis set. Multiple imputation method will be used to impute the missing outcome at each timepoint (24 hours  $\pm 4$ , 48 hours  $\pm 4$  hours, 72 hours  $\pm 4$  hours and 96 hours  $\pm 4$  hours) as described in Section 4.2.3 for clinical symptom improvement and resolution, respectively.

[figure not shown]
Counts and percentage of participants with “Clinical improvement with resolution outcome” at each timepoint and its corresponding 95% (Wald) CIs will be presented.

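### The imputation model for the ITT treatment-policy estimands has no term for missed doses or stopped gepotidacin, so it can pull the rate toward that of the mostly adherent women who are observed

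*SAP*

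**What the plan says.** **Estimands.** In SAP 1.1 the supplementary estimand for the primary endpoint handles failure to take two doses by treatment policy: "Interest lies in the treatment effect regardless of compliance with the study intervention". The supplementary estimands for the secondary endpoints do the same for less than 80% of doses ("Interest lies in all participants regardless of compliance with study intervention") and for stopping gepotidacin. The population line of the secondary supplementary estimand in SAP 1.1 still carries the 80% condition. However, its rationale, the ITT set assigned to it in SAP 3 and the protocol's Section 3 all point to every participant.

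**Main ITT analyses.** SAP 4.2.4 and 4.3.1.4 run these only above a redacted level of non-compliance. A missing CSS counts as failure.

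**Imputation.** For the ITT set, SAP 4.2.4.1 says "The multiple imputation method will be used to impute the Responders (participants who achieve clinical symptom improvement) at 24 hours", by steps 1 and 2 of SAP 4.2.3. SAP 4.3.1.5 says "Multiple imputation method will be used to impute the missing outcome at each timepoint" and also points to 4.2.3. Section 4.2.3 is a logistic regression under missing at random, specified for CE24, in which every woman took both doses. The covariate names are redacted, but the sentence introducing them is readable: "The following baseline covariates will be included in the imputation model". Women with a missing outcome and a qualifying antibiotic, and women with missing covariates, are set to non-improved. SAP 4.3.1.3 adds one redacted covariate for the CE48, CE72 and CE96 analyses; 4.3.1.5 does not cite that section.

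**The concern.** Doses missed or treatment stopped after Day 1 cannot be baseline covariates, and no term, stratum or delta is added when the CE24 model is moved to the ITT set. The model therefore assumes that, given baseline, a non-adherent woman without a CSS improves as often as the women who were observed, most of whom adhered. That is an assumption about the very intercurrent event that separates the ITT estimand from the CE one.

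At 24 h the design ties the two together. Under footnote o of the protocol's Schedule of Activities, the Visit 2 CSS is put off until the second dose has been taken. Under SAP Table 1, a CSS outside the window is undeterminable. Missed doses and missing scores will therefore tend to occur in the same women.

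The analysis runs only when non-compliance has passed the trigger, and it is the one alternative offered to counting missing as failure. A result close to the CE24 rate could be read as robustness to non-adherence when it partly reflects the model.

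**Working it through.** **The plan's own figure.** Protocol 1.1: "Approximately 90 participants will be enrolled in the study to ensure at least 82 evaluable participants are included in the primary analysis", "under an assumption that 74% of participants meet the primary endpoint criteria", with a target 95% CI half-width of about 10 points. The Clopper-Pearson interval for 61/82 = 74.4% is 63.6% to 83.4%, half-width 9.92 points; n = 81 gives 10.02. The 82 reproduces. The gap to 90 leaves 90 − 82 = 8 women outside CE24.

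**Inputs for the 24 h check**
- From the protocol: N = 90, adherent improvement rate 74%.
- Assumed, because the documents give no values: k non-adherent women (8 or 14), m of them without a CSS, and their improvement rate q (20% to 74%).
- Simplifications: all adherent women have a CSS, adherence is unrelated to the baseline covariates, and no antibiotic use is involved.

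**Formulas**
- Target (treatment policy) = [(90 − k) × 0.74 + k × q] / 90
- Pooled observed rate P = [(90 − k) × 0.74 + (k − m) × q] / (90 − m). This is also the expected imputed ITT rate.
- Bias of the planned imputation = m × (P − q) / 90
- Bias of counting missing as failure = −m × q / 90

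**Worked case: k = 8, m = 4, q = 40%**
- Target = (60.68 + 3.20) / 90 = 71.0%
- P = (60.68 + 1.60) / 86 = 72.4%
- Bias = 4 × (0.724 − 0.40) / 90 = +1.4 points
- With an adherence term: 71.0%, no bias in expectation
- Missing as failure: 62.28 / 90 = 69.2%, −1.8 points

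**Range**

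| k | m | q | Target | Planned imputation (bias) | Missing = failure (bias) |
|---|---|---|---|---|---|
| 8 | 4 | 20% | 69.2% | 71.5% (+2.3) | 68.3% (−0.9) |
| 8 | 4 | 60% | 72.8% | 73.3% (+0.6) | 70.1% (−2.7) |
| 8 | 4 | 74% | 74.0% | 74.0% (0) | 70.7% (−3.3) |
| 8 | 8 | 20% | 69.2% | 74.0% (+4.8) | 67.4% (−1.8) |
| 8 | 8 | 40% | 71.0% | 74.0% (+3.0) | 67.4% (−3.6) |
| 14 | 7 | 40% | 68.7% | 71.1% (+2.4) | 65.6% (−3.1) |
| 14 | 14 | 20% | 65.6% | 74.0% (+8.4) | 62.5% (−3.1) |
| 14 | 14 | 40% | 68.7% | 74.0% (+5.3) | 62.5% (−6.2) |

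**When no non-adherent woman is observed (m = k).** The planned imputation returns exactly 74.0% and an adherence term cannot be estimated. The planned bias is k(0.74 − q)/90 and the failure-rule bias is −kq/90. Failure is the closer of the two only when q is below 0.74 / 2 = 37%.

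The 74% is a 24 h planning value, so no figure is given for 48 to 96 h.

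**The case against.** A reader might infer that non-adherent women are imputed as if they had adhered, and that the ITT result must return the CE rate. The documents do not support that in general. Draws come from the pooled observed ITT women and match the adherent rate only if no non-adherent woman has a usable CSS, or if she improves just as often. At 24 h the first condition is plausible on the 20 to 28 h window. SAP Table 3 also lists an extended window of 12 to 36 h, and the readable text does not say how it is used. At 48 to 96 h the condition is less likely. Protocol 7.1 keeps women who stop treatment in follow-up, early-withdrawal visits before the end of treatment collect a CSS, and SAP 6.3.9 uses the available scores.

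Four further points stand:
- Upward bias needs non-adherent women to improve less often; at q = 74% there is none.
- Women who moved to another antibiotic, likely the poorest responders, are already failures, so very low values of q for the rest are doubtful.
- The main ITT analysis counts missing as failure and errs downward, so the plan already gives a low and a higher result.
- This is a conditional sensitivity analysis in a single-arm study with no hypothesis test, and the bias with 8 non-adherent lies within a CI half-width of about 9.5 points at N = 90.

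The redactions also limit what can be said. At 48 to 96 h the omission rests on 4.3.1.5 citing 4.2.3 rather than 4.3.1.3, and the extra covariate in 4.3.1.3 cannot be identified. None of this supplies an adherence term to a model described as baseline only.

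**Conclusion.** The point holds in limited form. On the readable text, the ITT imputation model ignores the intercurrent events that its estimands handle by treatment policy, and missing outcomes in non-adherent women lean toward those of the mostly adherent observed women.

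Under the stated assumptions the bias is about +1.4 points in the central case. It runs from 0 to +4.8 points with 8 non-adherent women and up to +8.4 with 14, the upper ends requiring q = 20% and no in-window CSS in any of them. Direction and size both depend on a response rate that the documents do not give. The primary CE24 analysis and the main ITT analyses are untouched. The change is worth making because it is cheap and because this analysis is produced only when non-adherence has become common enough to matter.

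**What to change.** In SAP 4.2.4.1 and 4.3.1.5:

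1. Add adherence status up to the time point to the imputation model: two doses taken yes/no at 24 h; a single term at 48, 72 and 96 h, such as at least 80% of doses taken and still on treatment yes/no. One combined term rather than two overlapping ones lowers the risk of separation in the logistic model.
2. Prespecify when too few non-adherent women have an observed CSS to estimate that term, which is likely at 24 h. In that case do not default to failure, which repeats the main ITT rule for these women. Impute them with a prespecified delta, or over a range of response rates running from failure up to the missing-at-random rate, and report the range.
3. Report CSS completeness by adherence at each time point.

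The cost is SAP wording, one model term and a little more analysis work. Compliance up to each time point is already derived for the CE sets (SAP 3), the intercurrent-event table (SAP 4.5.1) and the compliance summary (SAP 6.1.6). The interval will be wider, and the imputed rate somewhat lower if non-adherent women do worse.

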### **4.3. Secondary Endpoint(s) Analyses**

Estimands supporting secondary efficacy endpoints and Supplementary estimand (refer Section 1.1.) for secondary efficacy endpoints will be used for the secondary efficacy analysis.

#### **4.3.1. Secondary endpoint(s)**

The secondary efficacy endpoints and analyses are described in this Section.

- Achieving clinical symptom improvement, defined as a decrease from baseline of at least 1 point in the CSS total score at 48 hours ( $\pm$ 4 hours), 72 hours ( $\pm$ 4 hours), and 96 hours ( $\pm$ 4 hours), without the need for other systemic antimicrobials on or before the time of the assessments. A participant will be considered to have clinical improvement (including clinical resolution) outcome if they attain either a “Clinical Improvement with Clinical Resolution” outcome or, a “Clinical Improvement without Clinical Resolution” outcome as defined in Table 1. And otherwise, as not improved/failure if they have any other outcomes.
- Achieving clinical symptom resolution, defined as a decrease from baseline to a CSS total score of 0 at 24 hours ( $\pm$ 4 hours), 48 hours ( $\pm$ 4 hours), 72 hours ( $\pm$ 4 hours), and

96 hours ( $\pm 4$  hours), without the need for other systemic antimicrobials on or before the time of the assessments, as defined in [Table 1](#). A participant will be considered to have clinical symptom resolution if they attain an outcome (As defined in [Table 1](#)) of “Clinical Resolution”. They will be considered as not achieving clinical resolution for all other outcomes in [Table 1](#) (i.e. Clinical Improvement without Clinical Resolution, no change, clinical worsening and UTD).

#### **4.3.1.1. Definition of secondary endpoints**

The clinical symptoms improvement (with and without resolution) and clinical resolution responses of a participant at each timepoint will be programmatically determined as defined in [Table 1](#) of Section [4.1.3](#).

#### **4.3.1.2. Main analytical approach for secondary endpoints**

The secondary efficacy endpoints will be estimated by number and percentage for participants with clinical symptom improvement at each timepoint (48 hours  $\pm 4$  hours, 72 hours  $\pm 4$  hours, and 96 hours  $\pm 4$  hours) using CE48, CE72 and CE96 sets respectively.

Additionally, the secondary efficacy endpoints will also be estimated by the number and percentage of participants with clinical symptom resolution at each timepoint, 24 hours ( $\pm 4$  hours), 48 hours ( $\pm 4$  hours), 72 hours ( $\pm 4$  hours), and 96 hours ( $\pm 4$  hours) using CE24 , CE48 , CE72 and CE96 sets respectively, as described in Section [3](#).

Counts and percentage and Exact binomial (Clopper Pearson) 95% confidence limits for percentage of participants clinical symptom improvement and resolution at each timepoint will be computed.

Participants who are not able to complete the CSS assessment at each timepoint (48 hours  $\pm 4$  hours, 72 hours  $\pm 4$  hours and 96 hours  $\pm 4$  hours) will be considered as ‘treatment failure’ and included as not improved in the analysis of symptom improvement and not resolved in the analysis of symptom resolution.

A shift table will be created to explore the changes in the total CSS score and the individual symptoms score from baseline by visit. The analysis will be conducted on the ITT set at each timepoints (i.e. 24 hours ( $\pm 4$  hours), 48 hours ( $\pm 4$  hours), 72 hours ( $\pm 4$  hours), and 96 hours ( $\pm 4$  hours)).

#### **4.3.1.3. Sensitivity analyses for secondary endpoints**

Sensitivity analysis will be executed to investigate the robustness of the secondary efficacy outcomes (Outcomes are “Clinical Improvement with resolution” and “Clinical Resolution”).

This sensitivity analyses will measure the impact for those participants who are unable to complete the CSS assessment at each timepoint. Multiple imputation method will be used to impute the clinical outcome of interest at each timepoint (48 hours  $\pm 4$  hours, 72 hours

$\pm 4$  hours and 96 hours  $\pm 4$  hours) as described in Section 4.2.3. Step 1 & Step 2 with an additional covariate:

- **CCI**

Counts and percentage of participants with the outcome of interest at each timepoint and its corresponding 95% Exact Binomial CIs will be presented.

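### Two multiple-imputation sensitivity analyses (SAP 4.3.1.3 and 4.2.4.1) stop before Rubin pooling and name an exact binomial interval that cannot reflect the imputation

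*SAP*

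**What the plan says.** SAP 4.2.3, the sensitivity analysis of the primary estimand, sets out multiple imputation in three steps. Step 1 imputes missing outcomes by logistic regression. Step 2 derives the responder outcome in every dataset: "Step 1 will generate 1000 imputed datasets". Step 3 pools: "The estimated quantities in Step 2 will be combined across the imputed datasets using" Rubin's rules. The result "will be estimated and its corresponding 95% (Wald) CIs will also be presented".

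SAP 4.3.1.3 applies the method to the secondary endpoints at 48, 72 and 96 hours, with no trigger. It imputes "as described in Section 4.2.3. Step 1 & Step 2 with an additional covariate" and ends: "Counts and percentage of participants with the outcome of interest at each timepoint and its corresponding 95% Exact Binomial CIs will be presented".

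SAP 4.2.4.1 (supplementary estimand, ITT set) runs only if the threshold in 4.2.4 is met. It imputes "as described in Section 4.2.3. step 1 & step 2", and the percentage "will be estimated and its corresponding 95% Exact Binomial CIs will also be presented".

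The fourth such analysis, 4.3.1.5, refers to 4.2.3 without limiting the steps and reports Wald intervals. Protocol 9.3.3 leaves the imputation details to the SAP, so nothing upstream supplies a pooling rule. The one redaction inside 4.3.1.3 sits under the additional covariate, an unlikely place for one.

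**The concern.** An exact (Clopper-Pearson) interval is a function of one count out of one denominator. That suits the main analysis in 4.3.1.2, where missing assessments count as failures and there is a single count. After imputation there are 1000 counts, and the two sections leave out the step that would combine them.

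Two things follow. The analysis cannot be reproduced from the text, because several incompatible readings are possible. And every exact-binomial reading leaves out the between-imputation variance, so the reported precision does not reflect how much was imputed. That matters here because 4.3.1.3 exists to show what missing symptom scores do to the secondary results, and the SAP text is what will be programmed.

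**Working it through.** **Inputs.** From the documents: 82 evaluable, 74% improvement at 24 hours and a 95% CI half-width of about 10 points or less (Protocol 1.1); 1000 imputations (SAP 4.2.3). Assumed, because no readable text gives them: 4, 8, 16 or 25 of 82 missing (5, 10, 20, 30%), and true rates of 30, 50, 74, 90 and 95% to span the later timepoints.

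**The plan's own figure.** Clopper-Pearson limits are the 2.5% quantile of Beta(x, n−x+1) and the 97.5% quantile of Beta(x+1, n−x). With n = 82 and x = 0.74 × 82 = 60.68 the half-width is 9.97 points; at n = 81 it is 10.03. So 82 is the smallest size that meets the target, and it was evidently set with the exact interval. A Wald interval would have needed only 74. For one complete count, 61/82, the exact interval is 63.6–83.4% (half-width 9.92).

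**Worked case: 16 missing, 49 of the 66 observed improved.** Draw p from Beta(49.5, 17.5), then draw the 16 missing outcomes.

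- Mean imputed count = 49 + 16 × 49.5/67 = 60.82, so Q = 60.82/82 = 0.7417.
- Variance of the count = 16 × 0.7388 × 0.2612 × (67+16)/(67+1) = 3.77.
- Between-imputation variance B = 3.77/82² = 0.000560.
- Within-imputation variance W = [Q(1−Q) − B]/82 = 0.002329.
- Rubin: T = W + (1 + 1/1000)B = 0.002890. Half-width on the Wald scale = 1.96 × √0.002890 = 10.5 points. With B dropped it is 1.96 × √0.002329 = 9.5.

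Possible readings of an exact interval after Steps 1 and 2, for the same data:

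| Reading | 95% interval |
|---|---|
| Mean count, 60.8/82 | 63.3–83.2% (half-width 9.95) |
| One dataset (central 95% of counts: 57 to 64) | from 58.4–79.2% to 67.5–86.4% |
| All 82,000 stacked rows | half-width about 0.3 points |
| For comparison: Rubin on the logit scale | 62.2–83.0% (half-width 10.4) |

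The mean-count reading is the most sensible exact one, yet its half-width of 9.95 is practically that of 61/82 with nothing missing (9.92).

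**Half-width in points, n = 82, rate 74%:**

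| Missing | Exact on mean count | Rubin-logit | Rubin-Wilson |
|---|---|---|---|
| 4 | 9.9 | 9.6 | 9.5 |
| 8 | 9.9 | 9.8 | 9.8 |
| 16 | 9.9 | 10.4 | 10.3 |
| 25 | 9.9 | 11.1 | 11.0 |

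**Coverage of nominal 95% intervals.** Simulation with 5000 replicates per cell, 1000 imputations and outcomes missing completely at random; Monte Carlo error about 0.3–0.5 points.

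| Missing | Exact on mean count, all five rates | Rubin-Wald, rate 90% | Rubin-Wald, rate 95% |
|---|---|---|---|
| 4 | 94.9–96.8% | 95.0% | 90.2% |
| 8 | 94.5–95.7% | 93.6% | 88.6% |
| 16 | 93.6–94.5% | 89.3% | 83.7% |
| 25 | 90.9–92.3% | 92.2% | 94.0% |

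Rubin-Wald covers 92.0–95.4% at rates of 30–74%; its uneven pattern at high rates comes from discrete counts. Over all 20 cells Rubin-logit (0.5 added to both counts) covers 93.4–97.0% and Rubin-Wilson 94.0–96.9%.

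**Sensitivity to the set-up.** Predictive covariates shrink the effect. In a second run at 74% with 25 missing, exact coverage is 92.1, 93.0 and 93.4% for a covariate R² of 0, 0.13 and 0.30, against 96.0, 95.7 and 95.7% for Rubin-logit. Set size changes little. At n = 70 with 10% and then 30% missing, exact is 10.7 and 10.7 points against Rubin-logit 10.6 and 11.9. At n = 90 it is 9.4 and 9.4 against 9.4 and 10.6.

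**The case against.** The strongest reply is that the documents show an incomplete specification, not a particular faulty interval, and that the coverage figures describe only the mean-count reading. The second half is right. The fault itself does not depend on the reading, though: a mean count, a single dataset and stacked rows all leave out the between-imputation variance.

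It is also fair to say that the effect is small. At 74% the exact and Rubin-logit half-widths differ by 0.3, 0.1, 0.5 and 1.2 points across the four missing counts, and with 4 missing the exact interval is the wider one. The only readable planning loss is about 90 enrolled for 82 evaluable (8/90 = 8.9%). That figure concerns evaluability, so it does not bound missing scores, but it lends no support to 30%. Fewer outcomes may be imputed than are missing, because antibiotic users are set to failure and "Any participants who have a missing value for one or more model covariates listed above will be excluded from the imputation model", after which they too count as failures. Against that, SAP Table 1 treats out-of-window assessments as missing, so the fraction need not be trivial; whether those cases are imputed is not clearly stated.

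The SAP's own Rubin-Wald method is not reliably better than the exact interval, except near 30% missing. That stands, and it is why the remedy is not simply to copy 4.2.3. The high-rate weakness of Wald does rest on assumed rates, since no 48–96 hour rate is readable.

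Finally, no hypothesis test uses these intervals (SAP 2), and 4.2.4.1 may never run. Both points stand and limit the importance of the finding.

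**Conclusion.** The concern holds. Sections 4.3.1.3 and 4.2.4.1 omit the pooling step, name an interval that does not fit multiply imputed data, and do not determine which number will be reported. Sections 4.2.3 and 4.3.1.5 handle the same method differently, with no reason given.

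If the programmer takes the mean count, the loss is negligible up to about 10% missing, slight at 20% and clear only near 30%. If the rows were stacked, the interval would be far too narrow. These sizes rest on assumed missing fractions and later-timepoint rates, outcomes missing completely at random, and simple imputation models in place of the redacted covariates. The pooled sensitivity analysis of the primary estimand is unaffected. The change should be made because the stated interval is wrong for the method and correcting it is cheap, not because a main conclusion is at risk.

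**What to change.** In 4.2.4.1 and 4.3.1.3, cite Steps 1 to 3 of 4.2.3. Replace the exact binomial interval with a Rubin-pooled 95% interval, either computed on the logit scale and back-transformed, or of Wilson type using the Rubin variance. For the logit version, state a rule for imputed datasets with no successes or all successes, for example adding 0.5 to both counts; the Wilson-type version needs none. Report how many outcomes were imputed at each timepoint. Keep the exact interval for the main and supplementary analyses, which have one count.

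Optionally, use the same interval in 4.2.3 and 4.3.1.5 so that all four imputation analyses agree.

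The cost is two SAP sentences (four with the optional alignment), a few lines of code and slightly wider intervals when many outcomes are imputed. No new data are needed.
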